3. PLANNED ANALYSES

3.1. Interim Analyses

3.1.1. Part 1: Dose Escalation Phase

During dose escalation, no formal interim analysis will be performed. Data will be reviewed through data visualization tool to inform dose escalation decisions. The mTPI (modified Toxicity Probability Interval) design will be utilized to guide dose escalation/de-escalation decisions which is described in Section 3.1.1.1.

After the last cohort of patients in Part 1 complete the DLT observation period (21 days), a formal interim analysis will be performed to support the RP2D decision, except for scenarios where RP2D is clearly defined by the toxicity profile. Data considered to support RP2D decision will include but not limited to safety, available PK profile and observed signs of clinical activity. Details of the planned displays for RP2D are provided in a separate RAP.

3.1.1.1. Description of the Modified Toxicity Probability Interval

The mTPI design assumes the true underlying toxicity rate for maximum tolerated dose (MTD) of belantamab mafodotin falls within the range from 25% to 35% and centered at 30%. The monitoring rules for guiding dose escalations are provided in Table 1.

Columns provide the numbers of subjects treated at the current dose level, and rows provide the corresponding numbers of subjects experiencing toxicity. The entries of the table are dose-finding decisions (i.e., E, S, and D) representing escalating the dose, staying at the same dose, and de-escalating the dose. In addition, decision U means that the current dose level is unacceptable because of high toxicity; the current dose level and any higher dose level should be excluded from the trial. For example, when one of three subject's experiences toxicity, the decision can be located at row 1 and column 3, which is S – to stay at the current dose level. Consequently, the next cohort of subjects will be treated at the same dose level currently being used. If 0 of 3 subjects experiences toxicity, the decision is at row 0 and column 3, which is E – to escalate. Thus, the next cohort of subjects will be treated at the next-higher dose level. If three of three subjects experiences toxicity, the decision is DU – to de-escalate to the next-lower dose level, and exclude the current dose and any higher dose from the trial, because the high toxicity level is unacceptable. In dose escalation (E)/de-escalation (D), no dose skipping is allowed.

Table 1 Dose-Escalation Monitoring Rules for Part 1 Using the mTPI Method

Number of TDLTs	Number of Patients treated at current dose					
	1	2	3	4	5	6
0	E	E	E	E	E	E
1	D	S	S	S	S	E
2		DU	D	S	S	S
3			DU	DU	D	S
4				DU	DU	DU
5					DU	DU
6						DU

The Table was generated based on a beta/binomial model and precalculated before trial initiation. The letters in different colors are computed based on the decision rules under the mTPI method and represent different dose-finding actions. In addition to actions de-escalate the dose (D), stay at the same dose (S), and escalate the dose (E), the Table includes action unacceptable toxicity (DU), which is defined as the execution of the dose-exclusion rule in mTPI. Excerpted from Ji et al [Ji, 2010]

3.1.1.2. Displays To Be Created For Dose Escalation Review By Request

Review of preliminary data will be performed after completion of each dosing cohort in Part 1. Preliminary safety and study population data may include, if requested, a demographic characteristics summary, exposure of study drugs summary, adverse event (AE) summary by systems organ class (SOC) and preferred term (PT) and maximum grade, AE related to study treatment summary by maximum grade, AEs leading to dose modification by PT summary, serious adverse events (SAE) summary by SOC and PT, and listing of laboratory assessments with NCI-CTCAE Grade 3 and 4. Spreadsheets containing study data will be supplied by the study data manager.

Dose escalation/de-escalation decisions will take into account all available safety and tolerability data. The decisions will be informed by the mTPI approach and will occur following review of these data and joint discussion by the GSK Study Team and investigators. The details of the planned displays, if requested, are provided in [Appendix 11: List of Data Displays](#).

[figure not shown]
3.1.2. Part 2 Dose Expansion Phase

Continuous safety monitoring will be conducted for the expansion cohort starting from when 5 subjects are dosed. The observed number of treatment-related Grade 4 or higher AEs will be compared against the safety stopping rule in [Table 2](#). Enrollment may stop if the safety stopping rule is met based on totality of safety data. For example, if there are 3 events out of 5 dosed subjects, enrollment may stop after review of all safety data; if there is 2 or fewer events out of 5 dosed subjects, enrollment will continue. Operating characteristics for the safety stopping rule are provided in [Figure 1](#). The iSRC will review and may implement Part 2 safety stopping rules, if pre-specified criteria are met. Details of the planned analyses for the iSRC data review meetings, including subject demographic, subject disposition, AE and SAE data, are documented in a separate RAP.

Table 2 Safety Stopping Rules for the Expansion Cohort

Number of dosed subjects	Stop if treatment related Grade 4 or higher AEs larger or equal to this this number
5	3
6-10	4
11-14	5
15-19	6
20-25	7
26-28	8

Figure 1 Operating Characteristics of Safety Stopping Rule for Expansion Cohort

Interim analyses for ORR will start when at least 10 subjects are evaluable as defined in Section 4. Subjects who initially received RP2D in Part 1 may also be included. The observed number of subjects with unconfirmed response of PR or better will be compared with the stopping boundary in Table 3. Enrolment may stop if the stopping rule is met. Final decision will be based on the totality of data. For example, if there are 2 unconfirmed responses out of 10 evaluable subjects, enrolment may stop after review of all available data; if there are 3 or more unconfirmed responses out of 10 evaluable subjects, enrolment will continue. More details of the operating characteristics for futility analysis are provided in Section 3.1.2.1.

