Treatment Assignment	
 This is a non-randomized, single arm, open label, two-part study.
Interim Analysis	
 Part 1: Dose Escalation Phase 
 During the dose escalation, no formal interim analysis is planned for Part 1. Data will be reviewed through data visualization tool to inform dose escalation decisions. The mTPI design will be utilized to guide dose escalation/de-escalation decisions. After the last cohort of subjects in Part 1 complete the DLT observation period, a formal interim analysis will be performed to support the RP2D decision, except for scenarios where RP2D is clearly defined by the toxicity profile. Part 2: Dose Expansion Phase 
 Treatment-related Grade 4 or higher AEs will be continuously monitored starting from when 5 subjects are dosed. If observed toxicity level is significantly higher than 12% at 1-sided alpha of 0.025, the study may be terminated early based on totality of safety data. The 12% threshold is chosen based on 11% Grade 4 or higher AE observed in study BMA117159. Futility analyses for ORR will start when 10 subjects are evaluable. Enrollment may stop if the stopping rule is met based on totality of data. Stopping rules are provided in Section 3.1.2.1 of RAP. Primary Analysis 
 The primary analysis will take place approximately 15 months from the last subject first visit (LSFV). Further details can be referred to in Section 3 of RAP and Section 9.6 of the protocol (version: GSK Document Number TMF-14344600)

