2.4.2. Part 2: Expansion Cohort

The primary goal of Part 2 is to characterize clinical activity of the combination and to detect if meaningful response rate (ORR) can be achieved. Based on historical information [[Lokhorst](#), 2015] and clinical judgement, the null hypothesis has been defined as $ORR \leq 40\%$. The alternative hypothesis has been defined as $ORR \geq 60\%$ based on clinically meaningful improvement of 20%.

In Part 2, treatment-related Grade 4 or higher AEs will be continuously monitored starting from when 5 participants are dosed. Based on the 11% Grade 4 or higher AEs observed in the FTIH study (BMA117159), it is considered that the combination treatment has unacceptable toxicity if observed treatment-related Grade 4 or higher AEs is significantly higher than 12% at 1-sided alpha of 0.025.

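### The Part 2 safety stopping rule is worded as a count of adverse events, but Table 2 is a per-look binomial boundary for the number of subjects with an event

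*SAP*

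**What the plan says.** Section 2.3 sets the criterion: "If observed toxicity level is significantly higher than 12% at 1-sided alpha of 0.025, the study may be terminated early". Section 2.4.2 repeats it: toxicity is unacceptable if "treatment-related Grade 4 or higher AEs is significantly higher than 12% at 1-sided alpha of 0.025". Section 2.3 also gives the origin of the threshold: "The 12% threshold is chosen based on 11% Grade 4 or higher AE observed in study BMA117159".

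Section 3.1.2 makes the rule operational. On timing: "Continuous safety monitoring will be conducted for the expansion cohort starting from when 5 subjects are dosed". On the quantity compared: "The observed number of treatment-related Grade 4 or higher AEs will be compared against the safety stopping rule in" Table 2. The boundary column is headed "Stop if treatment related Grade 4 or higher AEs larger or equal to this this number" and is indexed by the number of dosed subjects. The example reads "if there are 3 events out of 5 dosed subjects, enrollment may stop after review of all safety data". The boundary is 3 at n = 5, 4 at 6–10, 5 at 11–14, 6 at 15–19, 7 at 20–25 and 8 at 26–28.

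The rule is not binding: enrolment may stop after the iSRC has reviewed the safety data as a whole. Operating characteristics are referred to Figure 1, which is not shown in the text available here.

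**The concern.** A binomial test against 12% needs a count that cannot exceed the number of subjects, with each subject contributing 0 or 1. A count of AEs has neither property, because one subject can contribute several. If the boundary was built for subjects and is applied to AEs, the test is no longer at the level stated, and by how much depends on how many qualifying AEs an affected subject has.

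The plan elsewhere keeps the two quantities apart. The dose-escalation text (3.1.1.1) speaks of subjects experiencing toxicity. The futility rule in the same Section 3.1.2 is defined on subjects with a response. Section 8.2.1.1 lists subjects with an event and number of events as separate items, and it plans categories for one, two, and three or more occurrences per subject. Repeat events within a subject are therefore expected.

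At stake is whether a crossing means that too many subjects are affected, or only that a few subjects each had several events.

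A second, smaller matter is that 0.025 is given without saying whether it applies at each look or over the whole of the continuous monitoring.

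**Working it through.** **Inputs.** Null rate 12% and one-sided 0.025 (SAP 2.3, 2.4.2). Monitoring from 5 dosed subjects and the Table 2 boundary b(n) (3.1.2). Maximum of 28 subjects (3.1.2.1). The mean number of qualifying AEs per affected subject is not given, so a range of 1 to 2 is assumed.

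**Step 1: reproduce Table 2.** For each n from 5 to 28, find the smallest k with P(X ≥ k) ≤ 0.025, where X ~ Binomial(n, 0.12). Examples:

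| n | P at one below the boundary | P at the Table 2 boundary |
|---|---|---|
| 5 | k = 2: 0.1125 | k = 3: 0.0143 |
| 10 | k = 3: 0.1087 | k = 4: 0.0239 |
| 28 | k = 7: 0.0435 | k = 8: 0.0145 |

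The result equals Table 2 at all 24 sample sizes, with tail probabilities from 0.0025 to 0.0243. Five alternatives each fail at one or more n: an 11% null, a score test, a continuity-corrected score test, and Beta(1,1) or Beta(0.5,0.5) posterior rules. Table 2 is thus the exact per-look boundary for a count of subjects.

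**Step 2: cumulative crossing, counting subjects.** Let f(n,k) be the probability of k affected subjects after n without an earlier crossing. Then f(n,k) = 0.88·f(n−1,k) + 0.12·f(n−1,k−1), and any mass with k ≥ b(n) is removed at each n from 5 to 28. The removed mass sums to 0.0558, or 5.6%. The same recursion gives 4.0% at a true rate of 11%, 30.7% at 20% and 73.9% at 30%.

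This treats every subject's outcome as known at each look. If events become known later, the figure falls. In the extreme case where nothing is known until all 28 are dosed, it is the single tail P(X ≥ 8 | 28, 12%) = 1.45%.

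**Step 3: literal AE counting.** Two consequences need no assumed mean.
- At n = 5 the boundary is 3, so one subject with three qualifying AEs meets it. At a true 12%, the chance of at least one affected subject among five is 1 − 0.88⁵ = 47%.
- At n = 10 the boundary is 4, so two subjects with two AEs each meet it. The chance of two or more affected subjects among ten is 34%.

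For the whole course, 12% of subjects were taken as affected, each with 1 + Poisson(m − 1) AEs, and a look was made after each subject from 5 to 28 (simulation):

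| Mean AEs per affected subject, m (assumed) | Chance of ever crossing |
|---|---|
| 1.0 | 5.6% |
| 1.1 | about 12% |
| 1.25 | about 20% |
| 1.5 | about 34% |
| 2.0 | about 55% |

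A geometric instead of a Poisson spread gives much the same: 34% at 1.5 and 52% at 2.0.

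**The case against.** **The context points to subjects.** A 12% toxicity level, and events set out of dosed subjects, read as proportions. The SAP uses similar shorthand elsewhere: Table 1 labels its rows by number of toxicities, while its text speaks of subjects. This stands as evidence of intent. It does not settle the text, because nothing says that a subject counts once, and the intent supports the correction.

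**The consequence is limited.** Crossing prompts an iSRC review that sees the underlying AE data. One subject with three Grade 4 events would be recognised there, and over-counting errs towards earlier review. The iSRC's separate analysis plan, not seen here, may also define the count. All this stands, and it limits the harm.

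**Two stronger readings are not supported.** A reader might infer that the rule as written triggers far too often. The documents do not show that. The size depends wholly on AEs per affected subject, which the SAP does not give, and at one AE each the figure is 5.6%, which is modest for a non-binding safety rule. A reader might also infer that the plan misstates its overall false-alarm rate. It does not: it nowhere calls 0.025 an overall level, and Figure 1 may show cumulative probabilities.

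**Timing.** This is the second amendment of the analysis plan and concerns final-analysis displays, so decisions on stopping enrolment appear to be past. The edit would then mainly put the record right on what the rule tested.

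**Conclusion.** The counting unit is wrong as written. Section 3.1.2, the Table 2 header and the example compare a number of AEs with a boundary that is, at all 24 sample sizes, the exact per-look binomial boundary for a number of subjects. Followed literally, the rule does not test the criterion set in Sections 2.3 and 2.4.2.

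The effect is nil if every affected subject has exactly one qualifying AE. It grows quickly above that: a mean of 1.1 already doubles the chance of crossing at a 12% subject rate. These sizes rest on the assumed 1 + Poisson spread and on looks after each subject from 5 to 28 with outcomes known.

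The 0.025 is a per-look level, and 5.6% is the cumulative figure under the same look schedule, lower with delayed events. That is a clarification to add and does not show a false statement in the plan.

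**What to change.** Reconcile the counting unit with the derivation of Table 2. In Section 3.1.2, the Table 2 header and the worked example, write: number of subjects with at least one treatment-related Grade 4 or higher AE. Align Sections 2.3 and 2.4.2 with this.

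Add that 0.025 is the per-look level. Unless Figure 1 already shows it, add that the cumulative probability of crossing at a true rate of 12% is about 5.6%, assuming a look after each subject from 5 to 28 with outcomes known at each look, and lower if events occur with delay.

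The Table 2 numbers can stay. Holding the cumulative level to 0.025 would need a per-look level of about 0.0113 and would cut the chance of crossing at a true 30% rate from 73.9% to 61.5%, and nothing in the SAP asks for that trade. The cost is SAP wording only.

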	OR 
 ○ progressed, OR ○ died, OR ○ discontinued treatment due to other reasons ● No skipping of participant is allowed, e.g., if the 11th treated participant does not meet one of the criteria above, the 12th treated participant will not be included even if one of the criteria is met for the 12th subject. 	
Pharmacokinetic (PK)	
 ● Participants in the All Treated population from whom at least one PK sample was obtained and analysed for belantamab mafodotin. 	
 ● PK
Pharmacodynamic (PD)	
 ● Participants in the All Treated population from whom at least one biomarker sample was obtained and analysed. 	
 ● PD/biomarker

Refer to [Appendix 11](#): List of Data Displays which details the population used for each display.

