7. EFFICACY ANALYSES

7.1. Part 1: Dose Escalation

7.1.1. Secondary Efficacy Analyses

7.1.1.1. Endpoint / Variables

BOR

Best Overall Response (BOR) is defined as the best confirmed response (stringent Complete Response [sCR] > Complete Response [CR] > Very Good Partial Response [VGPR] > Partial Response [PR] > Minimal Response [MR] > Stable Disease [SD] > Progressive Disease [PD] > Not Evaluable [NE]) from treatment start date until disease progression or initiation of new anti-cancer therapy, whichever is earlier, as assessed by the investigator per IMWG (2016). Details on derivation of confirmed response are provided in [Table 4](#).

ORR

Overall Response Rate (ORR), defined as the percentage of participants with a confirmed PR or better as the BOR (i.e., Partial Response [PR], Very Good Partial Response [VGPR], Complete Response [CR], and stringent Complete Response [sCR]), as assessed by the investigator per IMWG (2016).

ORR at interim analysis will be analysed based on confirmed responses, if available. However, in case a participant has achieved a response of PR or better at data cut, which was not confirmed due to the time constraints (too short timeframe for the next assessment), but with a potential to be confirmed through subsequent assessments after interim, the participant will also be considered as a responder; if the participant dies or discontinues study or starts other anti-cancer therapy prior to confirming the response, the participant will not be considered as a responder at IA.

Only the assessments from the start of treatment up to the earlier of confirmed disease progression or the start of new anti-cancer therapy will be considered. Only new systemic anti-cancer drugs taken are considered as anti-cancer therapy (radiotherapy and surgeries are not considered as systemic anti-cancer therapy for the purpose of this analysis).

Subjects with only assessments of Not Evaluable or missing response will be treated as non-responders; i.e. they will be included in the denominator when calculating the percentage.

Details on derivation of confirmed response are provided in [Table 4](#).

Table 4 Derivation of Confirmed Response

	Response at the First Time Point	Response at Subsequent Time Point¹	Confirmed Response at the First Time Point
1	sCR	sCR	sCR
2	sCR	CR	CR
3	CR	sCR/CR	
4	sCR/CR	VGPR	VGPR
5	VGPR	sCR/CR/VGPR	
6	sCR/CR/VGPR	PR	PR
7	PR	sCR/CR/VGPR/PR	
8	sCR/CR/VGPR/PR	MR	MR
9	MR	sCR/CR/VGPR/PR/MR	
10	sCR/CR/VGPR/PR/MR	SD	SD

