11	sCR/CR/VGPR/PR/MR	PD (any reason) OR No subsequent disease assessment: subject died or discontinued study or started new anti-cancer therapy before further adequate disease assessment	SD
12	sCR/CR/VGPR/PR/MR/PD (due to reasons other than imaging, i.e., plasmacytoma or bone lesion)	No subsequent disease assessment: subject has not died, discontinued from study or (except for PD) started new anti-cancer therapy; but as yet has no further adequate disease assessments	Unconfirmed sCR/CR/VGPR/PR/MR/PD Will be categorized as NE for ORR analysis. For ORR analysis in IA, the UC response (PR or better) will be counted as responder.
13	PD (due to reasons other than imaging, i.e., plasmacytoma or bone lesion)	PD (any reason) including PD after initiation of new anti-cancer therapy OR	PD

	Response at the First Time Point	Response at Subsequent Time Point¹	Confirmed Response at the First Time Point
		No subsequent disease assessment: subject died due to PD before further adequate disease assessment (including death due to PD after initiation of new anti-cancer therapy)	
14	PD (due to reasons other than imaging, i.e., plasmacytoma or bone lesion)	sCR/CR/VGPR/PR/MR/SD OR No subsequent disease assessment: subject died due to reasons other than PD before further adequate disease assessment OR No subsequent disease assessment: subject discontinued study before further adequate disease assessment	NE
15	SD	Any OR No subsequent disease assessment	SD
16	PD due to imaging (plasmacytoma or bone lesion)	Any OR No subsequent disease assessment	PD
17	NE or missing	Any OR No subsequent disease assessment	NE

1 Subsequent disease assessment is defined as the next adequate (not missing or NE) disease assessment following the first timepoint before (or on the same date of) start of new anti-cancer therapy except for confirmation of PD, for which PD or death due to PD after new anti-cancer therapy are considered for confirmation of PD. No minimal time interval is required for the subsequent disease assessment but a different sample is required for confirmation.

2 SD does not need to be confirmed.

3 PD due to imaging (i.e., plasmacytoma or bone lesion) does not need to be confirmed.

Where criteria are not mutually exclusive, take the first that applies.

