7.2.1.3. Population of Interest

At futility interim, the primary efficacy analysis of ORR will be based on the All Evaluable population.

Otherwise, the primary efficacy analysis of ORR will be based on the All Treated population, unless otherwise specified.

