No.	Population	IDS / Example Shell	Title	Programming Notes	Deliverable [Priority]
1.0015	All Evaluable	DM1	Summary of Demographic Characteristics	Report for: futility interim analyses for part 2 participants and part 1 participants who initially received the RP2D (Refer to Section 5.1 for ordering of dose level). Add the following footnote: A subject is evaluable for interim analysis if the subject fulfils the criteria for 'All Treated' population with adequate baseline assessment and measurable disease meet at least one of the following criteria: if the planned assessment is every 3 weeks and at least three assessments are required, the time from the first dose to the time of data cut-off is more than 66 days, OR had an unconfirmed response of PR/CR or better, progressed, OR died, OR discontinued treatment due to other reasons	IA [1]
1.0016	Enrolled	DM11	Summary of Age Ranges	Include columns "No Treatment", "Part 1", "Part 2", "All Treated", "Total"	P-SAC [3], F-SAC [4]

Study Population Tables					
No.	Population	IDSL / Example Shell	Title	Programming Notes	Deliverable [Priority]
1.0017	All Treated	DM6	Summary of Race and Racial Combinations	Report for: Part 1, Part 2, and combined Part 1 and Part 2; Summarize by: dose level (Refer to Section 5.1 for ordering of dose level and omit 1.92 mg/kg if data is not available) Total.	P-SAC [3], F-SAC [4]
Prior and Concomitant Medications					
1.0018	All Treated	MH1	Summary of Current Medical Conditions	Report for: Part 1, Part 2, and combined Part 1 and Part 2; Summarize by: dose level (Refer to Section 5.1 for ordering of dose level and omit 1.92 mg/kg if data is not available) Total.	P-SAC [3], F-SAC [4]
1.0019	All Treated	MH1	Summary of Past Medical Conditions	Report for: Part 1, Part 2, and combined Part 1 and Part 2; Summarize by: dose level (Refer to Section 5.1 for ordering of dose level and omit 1.92 mg/kg if data is not available) Total.	P-SAC [3], F-SAC [4]
1.0020	All Treated	CM8	Summary of Concomitant Medications by Ingredient	Report for: Part 1, Part 2, and combined Part 1 and Part 2; Summarize by: dose level (Refer to Section 5.1 for ordering of dose level and omit 1.92 mg/kg if data is not available) Total.	P-SAC [3], F-SAC [4]

Study Population Tables					
No.	Population	IDSL / Example Shell	Title	Programming Notes	Deliverable [Priority]
Exposure and Treatment Compliance					

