3.0078	All Treated	LVEF1A	Summary of Left Ventricular Ejection Fraction Change from Baseline	Report for: Part 1, Part 2, and combined Part 1 and Part 2; Summarize by: dose level (Refer to Section 5.1 for ordering of dose level and omit 1.92 mg/kg if data is not available), Total; Worst case post-baseline only Footnote: LLN: Normal Range Lower Limit.	P-SAC [3], F-SAC [4]

Safety: Tables					
No.	Population	IDSL / Example Shell	Title	Programming Notes	Deliverable [Priority]
Dose Modifications					
3.0079	All Treated	ODMOD1	Summary of Dose Reductions of GSK2857916	Report for: Part 1, Part 2, and combined Part 1 and Part 2; Summarize by: dose level (Refer to Section 5.1 for ordering of dose level and omit 1.92 mg/kg if data is not available), Total;	P-SAC [3], F-SAC [4]
3.0080	All Evaluable	ODMOD1	Summary of Dose Reductions of GSK2857916	Report for: futility interim analyses for part 2 participants and part 1 participants who initially received the RP2D (Refer to Section 5.1 for ordering of dose level); Include the following footnote: "Note: A subject is evaluable for interim analysis if they meet at least one of these criteria: (More than 66 days in study and had at least three disease assessments) OR had at least one disease assessment on or after day 60 OR had an unconfirmed response of PR/CR or better OR progressed OR died OR discontinued treatment."	IA [1]

Safety: Tables					
No.	Population	IDSL / Example Shell	Title	Programming Notes	Deliverable [Priority]
3.0081	All Treated	ODMOD3	Summary of Dose Delays of GSK2857916	Report for: Part 1 and Part 2, and combined Part 1 and Part 2; Summarize by: dose level (Refer to Section 5.1 for ordering of dose level and omit 1.92 mg/kg if data is not available), Total; Include summary statistics. Include the following footnote: "Note: The protocol allows a window of \pm 3 days for administration of study treatment after Cycle 1 so a dose will only be considered delayed if it is 4 or more days after the scheduled dose date."	P-SAC [3], F-SAC [4]

Safety: Tables					
No.	Population	IDSL / Example Shell	Title	Programming Notes	Deliverable [Priority]

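### The futility rule is stated inconsistently: Section 3.1.2 and Section 7.1.1.1 count different responders, and display footnotes redefine who is evaluable, so the same data can fall on either side of the Table 3 boundary

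*SAP*

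**What the plan says.** **Responder at the look.**
- Section 3.1.2: "The observed number of subjects with unconfirmed response of PR or better will be compared with the stopping boundary in Table 3". Its worked example at 10 subjects is also in terms of unconfirmed responses: 2 may stop, 3 or more continue.
- Section 7.1.1.1: "ORR at interim analysis will be analysed based on confirmed responses, if available". An unconfirmed PR or better is added only if time was too short to confirm it and it still can be confirmed. For a subject who dies, discontinues the study or starts other anti-cancer therapy, "prior to confirming the response, the participant will not be considered as a responder at IA".
- Table 4: rows 10 and 11 turn a PR or better followed by SD, PD, death, discontinuation or new therapy into SD. Row 12 covers the pending case, and there "For ORR analysis in IA, the UC response (PR or better) will be counted as responder".
- Section 7.2.1.1 takes the Part 2 ORR definition from Section 7.1.1.1, and Section 7.2.1.3 says "At futility interim, the primary efficacy analysis of ORR will be based on the All Evaluable population". So the Section 7 rule does reach the futility look.

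**Evaluable subjects.**
- Section 3.1.2 refers to Section 4. Section 4 accepts more than 66 days from first dose to cut-off, an assessment on or after day 60, or one of several events. It has no measurable-disease condition, and "No skipping of participant is allowed".
- The footnote to Table 2.002, the futility response display, describes treated subjects "with adequate baseline assessment and measurable disease meet at least one of the following criteria" and leaves out the day-60 criterion. Tables 1.0015, 1.0022, 1.0025, 1.0027, 3.008, 3.0025 and 3.0027 carry the same text.
- The footnotes to the All Evaluable dose-modification tables (3.0080, 3.0082, 3.0084, 3.0086, 3.0088) give a third version: "More than 66 days in study and had at least three disease assessments", with day 60 restored and no measurable-disease condition.

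**The concern.** A pre-specified stopping boundary needs one count over one set of subjects. Here the section that states the rule and the section that defines the endpoint give different counts, and the footnote on the table that would show the result describes a different denominator from Section 4. Near the boundary the choice of text decides whether it is met.

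The columns of Table 3 are labelled by ORR, which the SAP defines as confirmed PR or better. If the look counts responses that never confirm, the counted event is more likely than confirmed ORR. The look is then more lenient than the table indicates. What is at stake is the futility decision and the expected number of subjects enrolled.

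**Working it through.** **1. Reproduce the plan's figures.** Inputs from Section 3.1.2.1: the Table 3 boundaries applied after each subject from 10 to 27, a maximum of 28, and success at 15 or more of 28 (Table 3 fails 14 or fewer). Each subject is one draw with probability p = ORR. First row at p = 0.40:

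P(continue at 10) = 1 − [0.6^10 + 10(0.4)(0.6^9) + 45(0.4^2)(0.6^8)] = 1 − (0.0060 + 0.0403 + 0.1209) = 0.833.

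Table 3 states 83.3%. Carrying the exact recursion through to n = 27 matches every row for n = 10 to 27 to 0.1 point. It gives early termination of 86.1% at 40% and 15.5% at 60% (stated 86.1% and 15.6%), type I error 0.0997 and power 0.806. Expected sample size comes out at 19.1 and 27.0 (stated 20 and 28); nothing below turns on that difference.

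**2. Same data, two responder rules.** Ten evaluable subjects, three with a PR, one of whom dies or progresses before confirmation.
- Section 3.1.2: 3 of 10, above the boundary of 2, so continue.
- Section 7.1.1.1 (death) or Table 4 row 11 (death or PD): 2 of 10, boundary met.

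Exactly 3 of 10, where reclassifying one subject changes the result, has probability 120 × 0.4^3 × 0.6^7 = 21.5% at 40%, and 120 × 0.6^3 × 0.4^7 = 4.2% at 60%.

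**3. Same data, two evaluable definitions.** Three responses so far. The 12th subject has SD assessed on day 61, cut-off is day 62, and no other criterion is met.
- Section 4: evaluable through the day-60 criterion, so 3 of 12; boundary 3 or fewer, met.
- Table 2.002 footnote: not evaluable, so 3 of 11; boundary 2 or fewer, not met.

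**4. Illustration of the responder effect.** Let e be the share of subjects with a response that never confirms. The SAP gives no value; 0.05 and 0.10 are assumed. The look counts with probability p + e (Section 3.1.2 read literally), and the final analysis counts with probability p. Exact three-outcome recursion:

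| Confirmed ORR | e | Early stopping | Expected N | P(15 or more confirmed of 28) |
|---|---|---|---|---|
| 40% | 0 | 86.1% | 19.1 | 0.100 |
| 40% | 0.05 | 71.0% | 21.7 | 0.101 |
| 40% | 0.10 | 51.3% | 24.0 | 0.102 |
| 60% | 0 | 15.5% | 27.0 | 0.806 |
| 60% | 0.05 | 6.0% | 27.6 | 0.811 |
| 60% | 0.10 | 1.7% | 27.9 | 0.813 |

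With no futility stopping at all, P(15 or more of 28) is 0.102 at 40% and 0.813 at 60%. That is the ceiling for the last column.

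**The case against.** The strongest reply is that the SAP already fixes both quantities. Section 3.1.2 sends the denominator to Section 4, and every interim display names All Evaluable as its population, so the footnotes are inaccurate notes rather than rival definitions. Table 4 row 12 uses the term unconfirmed for the pending case only, and Section 3.1.2 may be shorthand for that. The rule is also non-binding: enrolment may stop, and the final decision rests on the totality of data.

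Much of this stands. Section 4 is the controlling definition. The dose-modification tables (3.0080 to 3.0088) are displays and do not feed the boundary, and their wording echoes the reference to three assessments in Section 4 itself. Omitting day 60 matters only for a subject in a window of a few days. Whether the measurable-disease condition would ever remove anyone depends on eligibility criteria in the protocol, which is not shown.

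Two things survive. Nothing in Section 3.1.2 limits its count to pending responses or refers to Section 7.1.1.1. And the discretion comes after the boundary has been evaluated, so it does not settle which count to evaluate.

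A reader might go further and infer that the Table 3 probabilities do not apply, or that false-positive control is lost. The documents support neither. The table is correct for a response with the stated probability and holds approximately under the Section 7.1.1.1 rule when few responses are pending, while the final type I error stays near 0.10.

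**Conclusion.** The futility rule is wrong as written, in a limited way. The responder count differs between Section 3.1.2 and Section 7.1.1.1 with Table 4, and one reclassified subject in ten is enough to change the result. The denominator is properly fixed in Section 4 but misdescribed in the footnotes, including the one on the futility response table.

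The Table 3 probabilities hold only when the counted response has probability equal to the ORR in the column heading. The shifts in early stopping (86.1% to 71.0% or 51.3% at 40%; 15.5% to 6.0% or 1.7% at 60%) are illustrations. They rest on an assumed 5 or 10 points of never-confirmed responses and on the literal reading of Section 3.1.2. They cut both ways: fewer stops for an inactive combination, and fewer wrong stops for an active one. Type I error and power are essentially untouched.

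A reader might also infer that more patients were in fact exposed. The SAP does not show that. The current amendment changes only the final-analysis displays, and its footnotes already refer to subjects moving to post-analysis continued treatment, so enrolment was probably complete. The remaining value of the correction then lies in reporting the looks clearly.

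**What to change.** - In Section 3.1.2, use the Section 7.1.1.1/Table 4 interim rule: count a response that is confirmed, or unconfirmed and still pending, and never one already shown not to confirm. Reword the example at 10 subjects to match.
- Put the Section 4 definition verbatim in every All Evaluable footnote in Appendix 11. This removes the added baseline and measurable-disease condition, restores the day-60 criterion, and replaces the version in the dose-modification tables.
- Under Table 3, state that the probabilities refer to the response counted at the look and are approximate for confirmed ORR while responses are pending. This is still needed after the first change, because counting pending responses can put the interim probability above confirmed ORR.
- If looks have already taken place, report in the study report which responder and evaluable definitions were used at each.

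The cost is SAP wording and footnotes only. Compared with counting every unconfirmed response, the rule meets the boundary more often, at 60% as well as at 40%; with no pending responses this returns to the rates Table 3 states.
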